7.5.2.2.2 The frequency and magnitude of anti-drug antibodies targeting DZIF-10c

The same assessments will be performed as described in [Section 7.5.2.1.2](#).

This endpoint will be evaluated on the subject set TS.

7.5.2.2.3 SARS-CoV-2 RNA shedding in nasopharyngeal swabs determined by qRT-PCR in SARS-CoV-2-infected individuals

All evaluations for the first 7 days after drug administration will be done on the mITT set and will take data into consideration based on the time window around the corresponding visit as defined in [Section 6.7](#). The latest day to be taken into account is 7 days after drug administration. The evaluations for the later time points will be based on all subjects in the subject set TS who have at least a baseline value and a second measurement in the respective time period of viral RNA shedding in NP swabs by qRT-PCR.

Absolute viral load in SARS-CoV-2-infected individuals, as well as absolute and relative changes from baseline, will be summarised descriptively for each assessment time point and plotted by treatment arm and listed.

Time-weighted average change in viral load

The evaluation of viral load will be done by a time-weighted average change in \log_{10} viral load from baseline, defined by:

$$\frac{\sum_{i=a}^{b-1} \{0.5 * (Y_i + Y_{i+1}) * (t_{i+1} - t_i)\}}{(t_b - t_a)}$$

where

- Y_i = change from baseline in \log_{10} viral load at visit i
- t = time at the specified time point (the actual study day)
- a = baseline assessment at day 1
- b = last assessment at or prior to the threshold day (7 days after drug intake)

A parametric analysis of covariance (ANCOVA) model with corresponding baseline viral load and antibody status will be used. Adjusted means and 95% confidence intervals (CIs) will be provided. Missing values will not be imputed and since a linear trajectory on the log scale is expected, the normalisation by the denominator assures comparability of the values if t_b is different between patients.

Ratios between means (DZIF-10c vs placebo) will be calculated for each treatment arm separately for the respective time period. These calculations will be based on the mean time-weighted average change in viral load based on the ANCOVA model. CIs for the ratios will be reported for which the Delta method (Taylor method) will be used to calculate the variance of the ratios.

Mixed effect Model for Repeated Measures (MMRM)

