In addition to a time-weighted average change, changes from baseline will also be evaluated using a restricted maximum likelihood (REML) based repeated measures approach. Analyses will include the fixed, categorical effects of antibody status, and treatment-by-visit interaction, as well as the continuous, fixed covariates of baseline and baseline-by-visit interaction. An unstructured (co)variance structure will be used to model the within-subject measurements. In

case the model does not converge, other covariance structures will be used sequentially until convergences is reached and the used covariance structure will be reported. The sequence of covariance structures to be used is as follows: unstructured, antedependence, heterogeneous Toeplitz, Toeplitz, heterogeneous AR(1). The Kenward-Roger approximation will be used to estimate denominator degrees of freedom.

All model-based evaluations (time-weighted average change and MMRM) will be done for the following time periods:

- first 7 days after drug administration
- first 14 days after drug administration
- first 28 days after drug administration

Note that only data points within the analysis periods are considered. Data available after the cut-offs will not be considered for the model based evaluations.

All model-based evaluation will be done for the SARS-CoV-2 E gene. As sensitivity analyses, the evaluations will be repeated for the additionally assessed SARS-CoV-2 gene (ORF1a/b gene). This sensitivity analysis will be done on subjects from the subject set TS who have at least a baseline value and a second measurement in the respective time period of viral RNA shedding in OP swabs by qRT-PCR.

Clearance rate

It will be shown how many patients fell below the limit of valid quantification. Finally, the proportions of participants with positive and negative PCR for each assessed SARS-CoV-2 gene assessed at every given visit will be described (clearance rate). Missing data will not be imputed. Consequently, the number of patients with non-missing data will be used as denominator for each proportion. CIs for the proportions will be derived as Clopper-Pearson intervals.

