7.6.2.1 Successful virus isolation from nasopharyngeal swabs in SARS-CoV-2-infected individuals

Information will be shown for each assessment time point on whether live virus could be isolated in participating subjects or not. In addition, the relative frequency of positive samples will be shown per timepoint.

This endpoint will be evaluated on subjects from the subject set TS.

7.6.2.2 SARS-CoV-2 RNA shedding in oropharyngeal swabs determined by qRT-PCR in SARS-CoV-2-infected individuals

The same evaluations as proposed to be done for the secondary endpoint of SARS-CoV-2 RNA shedding in nasopharyngeal swabs determined by qRT-PCR in SARS-CoV-2-infected individuals shown in [Section 7.5.2.2.3](#) will be implemented for this endpoint. These evaluations will be based on all subjects in the subject set TS who have at least a baseline value and a second measurement in the respective time period of viral RNA shedding in OP swabs by qRT-PCR.

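### In SAP 7.5.2.2.3 the ORF1a/b repeat of the nasopharyngeal analysis is assigned to a population defined by oropharyngeal swabs, which contradicts the section's own rule and leaves the specimen to be analysed unclear

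*SAP*

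**What the plan says.** The section is headed "7.5.2.2.3 SARS-CoV-2 RNA shedding in nasopharyngeal swabs determined by qRT-PCR in SARS-CoV-2-infected individuals". It sets its population by period. For the first week, "All evaluations for the first 7 days after drug administration will be done on the mITT set", and SAP 6.3 defines mITT by a baseline and a second NP measurement within 7 days of drug intake. For longer periods, "The evaluations for the later time points will be based on all subjects in the subject set TS", restricted to those with a baseline and a second NP value in the period.

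On the gene, "All model-based evaluation will be done for the SARS-CoV-2 E gene". The same models (time-weighted average change and MMRM, over 7, 14 and 28 days) are then repeated for ORF1a/b as sensitivity analyses. The sentence that follows limits this repeat to treated-set participants "who have at least a baseline value and a second measurement in the respective time period of viral RNA shedding in OP swabs". It makes no distinction by period.

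SAP 7.6.2.2, the OP endpoint for phase IIa, applies the evaluations of 7.5.2.2.3 to OP swabs and gives its own population rule: "These evaluations will be based on all subjects in the subject set TS who have at least a baseline value" and a second OP measurement in the period.

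**The concern.** A repeat on a second gene target is useful when the gene is the only thing that changes. Here the population rule changes with it, from NP availability to OP availability. For the 7-day window the rule also conflicts with the section's statement that every evaluation in that window uses mITT; a programmer cannot follow both sentences.

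The sentence has two literal readings: NP ORF1a/b data in participants selected by their OP swabs, or OP ORF1a/b data. The example code in SAP 9.2.1.1 computes the time-weighted average separately by swab type and gene, so it accommodates either reading and does not settle the question.

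What is at stake is the check on NP viral load, a secondary endpoint. Protocol 8.1.4 calls the time-weighted average change in viral RNA shedding the main efficacy analysis, and SAP 9.1.2.1 says the phase IIa viral load results are to inform later development.

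**Working it through.** The plan gives no figure on this point to reproduce. The check is a comparison of the SAP's population rules, followed by an estimate of scale.

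**Step 1. The swab-specific rules side by side.**

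| SAP section | Endpoint swab | Analysis | Population rule | Swab in rule |
|---|---|---|---|---|
| 7.5.2.1.3 | NP | phase I | TS, baseline + second value | NP |
| 7.5.2.2.3 | NP | phase IIa, 7 days | mITT (SAP 6.3) | NP |
| 7.5.2.2.3 | NP | phase IIa, later periods | TS, baseline + second value | NP |
| 7.5.2.2.3 | NP | phase IIa, ORF1a/b repeat | TS, baseline + second value | **OP** |
| 7.6.1.2 | OP | phase I | TS, baseline + second value | OP |
| 7.6.2.2 | OP | phase IIa | TS, baseline + second value | OP |

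Five of the six rules match their own endpoint; only the ORF1a/b repeat does not. SAP Section 4 (additions, changes, clarifications) does not explain the exception. Because 7.6.2.2 already carries the same evaluations over to OP swabs, an OP rule is not needed in 7.5.2.2.3. That points to carried-over wording, though this is an inference.

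**Step 2. Who could be affected if NP data are analysed.** A participant with usable NP data is lost only if the OP baseline is missing or there is no OP value at all later in the period. Missing some OP swabs excludes nobody. Protocol 5.2.3 requires both swabs before dosing, and Appendix II B marks both central-laboratory swabs at the same visits.

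**Step 3. Scale.** The documents give no rates of missing swabs, so these are assumptions: a share mb of baseline swabs missing (0 to 10%), a share m of each later swab missing (5 to 20%), and NP and OP missing independently. With k non-optional visits after baseline (3, 4 or 5 for 7, 14 or 28 days), the probability of meeting one swab's rule is

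p = (1 − mb)(1 − m^k)

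and the expected number of the 60 Group 2D participants (Protocol 8.2) who meet the NP rule but not the OP rule is 60 × p × (1 − p).

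For 7 days (k = 3):

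| mb | m | p | 60 × p × (1 − p) |
|---|---|---|---|
| 0 | 5% | 0.9999 | 0.01 |
| 0 | 20% | 0.9920 | 0.48 |
| 2% | 5% | 0.9799 | 1.18 |
| 5% | 5% | 0.9499 | 2.86 |
| 10% | 10% | 0.8991 | 5.44 |
| 10% | 20% | 0.8928 | 5.74 |

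Worked example, last row: p = 0.90 × (1 − 0.20³) = 0.90 × 0.992 = 0.8928, and 60 × 0.8928 × 0.1072 = 5.74. With the same rates the result is 5.47 at 14 days and 5.41 at 28 days. If NP and OP swabs are always missed together, it is 0 in every period. The missing-baseline rate drives the result; with complete baselines the loss is below one participant.

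**Step 4. If OP data are analysed.** The repeat then differs from the E-gene analysis in specimen as well as gene, and no NP ORF1a/b model is fitted.

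**Step 5. After correction.** With the NP rule and the E-gene set in each period, differences caused by the population rule are 0 of 60 by construction.

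**The case against.** The strongest reply is that the mismatch may have no practical effect. The swabs are paired, a missed visit removes both, and one later value is enough for entry, so the two sets could be identical. The higher figures above need missing baseline swabs and independent missingness, and the documents support neither. This stands: a change in membership is possible, not shown.

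Three stronger readings are tempting and are not supported:

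- *The treated set is itself a second departure.* At 14 and 28 days the E-gene analysis also uses it. At 7 days mITT is in effect the treated Group 2D participants with two NP values, so membership differs through the swab condition. One qualification: Protocol 8.1.1 analyses mITT as randomised, whereas SAP 6.1 analyses as treated unless stated otherwise, so grouping could differ for anyone given the wrong treatment.
- *Participants with OP but without NP data are admitted.* If NP data are analysed, they have no NP change from baseline to contribute. They enter only if OP data are analysed.
- *The repeat cannot test robustness or is uninterpretable.* Agreement on a second gene in a slightly different set would still support the E-gene result. What is lost is attribution of a disagreement.

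It can also be said that the effect on the trial is small: SAP 7.5 plans no formal testing and treats p-values as nominal, the E-gene models are untouched, and the clearance-rate analysis covers each assessed gene separately. This also stands, and it limits the weight of the point. It does not remove the contradiction.

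**Conclusion.** The point holds as a specification error of limited impact. The ORF1a/b repeat in an NP section carries an OP population rule, conflicts with that section's own rules, and does not say which swab data are analysed. If NP data are analysed, the loss is unknown: 0 if swabs are missed together, and up to about 5.7 of 60 at 7 days under the least favourable rates assumed here. If OP data are analysed, the intended NP check is absent. Under either reading a disagreement with the E-gene result could not be put down to the gene target. The textual mismatch is certain; its origin in the OP section is probable; its numerical effect is not known from the documents. It should be corrected because two instructions conflict and the correction is simple.

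**What to change.** Replace the population sentence for the ORF1a/b repeat with wording to this effect:

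*The ORF1a/b sensitivity analysis uses nasopharyngeal data and the same participants as the E-gene analysis in each period: the mITT set for the first 7 days, and treated participants with a baseline and a second nasopharyngeal value in the period for 14 and 28 days.*

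Leave the OP population rule to 7.6.2.2, which already states it. The sponsor should confirm the intent first. If an OP-based repeat was meant, the SAP should say so, name the data analysed, give the reason, and reconcile it with the rule that all 7-day evaluations use mITT.

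The cost is one sentence of SAP text. No new data, visits or models are needed.

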7.6 FURTHER ENDPOINTS

The same further endpoints have been defined for both parts of the trial. Due to the nature of the different trial parts, there will however be differences in the analysis of those endpoints.

7.6.1 Further endpoints phase I

7.6.1.1 Successful virus isolation from nasopharyngeal swabs in SARS-CoV-2-infected individuals

Information will be shown for each assessment time point on whether live virus could be isolated in participating subjects or not, for each cohort and overall. In addition, the relative frequency of positive samples will be shown per timepoint.

This endpoint will be evaluated on subjects from the subject set TS.

7.6.1.2 SARS-CoV-2 RNA shedding in oropharyngeal swabs determined by qRT-PCR in SARS-CoV-2-infected individuals

Summary statistics of CT values as well as copies/ml based on a reference standard will be shown for each assessment time point, by cohort and overall. This will be done for absolute values as well as relative and absolute change from baseline. All assessments will be calculated separately for the assessed SARS-CoV-2 genes (E gene and the ORF1a/b gene).

These evaluations will be based on all subjects in the subject set TS who have at least a baseline value and a second measurement in the respective time period of viral RNA shedding in OP swabs by qRT-PCR.

7.6.1.3 Successful virus isolation from oropharyngeal swabs in SARS-CoV-2-infected individuals

Information will be shown for each assessment time point on whether live virus could be isolated in participating subjects or not, for each cohort and overall. In addition, the relative frequency of positive samples will be shown per timepoint.

This endpoint will be evaluated on subjects from the subject set TS.

7.6.1.4 Frequency of COVID19-related hospitalization and medically-attended health care contacts in SARS-CoV-2-infected individuals not previously hospitalized

Summary statistics will be shown for each assessment time point and in total, by cohort and overall.

This endpoint will be evaluated on subjects from the subject set TS.

7.6.1.5 Time to resolution of self-assessed SARS-CoV-2-related symptoms

Summary statistics will be shown for each assessment time point, by cohort and overall.

This endpoint will be evaluated on subjects from the subject set TS.

7.6.1.6 Differences of viral spike gene sequences obtained before and after study drug administration and the investigation of the effect of observed mutations on viral sensitivity to DZIF-10 in neutralization assays

Differences in gene sequences will be reported descriptively for cohorts including SARS-CoV-2-infected individuals (i.e. cohorts 2A-2Ds). Summary statistics, i.e. absolute values as well as relative and absolute change from baseline of IC50 and IC100 values against selected viral variants will be reported by cohort and overall.

These analyses will be performed by UKK and reported in a separate report which will be appended to the CTR.

7.6.1.7 The activity and frequency of SARS-CoV-2-reactive immune cells following DZIF-10c administration

As described in Section 4, these analyses will be performed by UKK and will not be included in the CTR but might be reported elsewhere.

7.6.1.8 Subgenomic SARS-CoV-2 mRNA levels in respiratory samples in SARS-CoV-2-infected individuals

Summary statistics (absolute values as well as relative and absolute change from baseline) will be shown for each assessment time point and dose cohort.

These analyses will be performed by UKK and reported in a separate report which will be appended to the CTR.

7.6.1.9 The pharmacokinetic profile of DZIF-10c, including elimination half-life, peak serum concentration, area under the curve, clearance, and volume of distribution

The PK parameters listed as further endpoints in [Section 5.3.9](#) will be derived according to the relevant BI internal procedure. Further PK parameters may be calculated, if considered reasonable (these parameters will be considered exploratory). Serum concentrations and PK parameters of DZIF-10c will be listed and analysed descriptively. If the number of subjects included allows, the following descriptive statistics will be calculated for analyte concentrations as well as for all pharmacokinetic parameters: N, arithmetic mean, standard deviation, minimum, median, maximum, P10, Q1, Q3, P90, arithmetic coefficient of variation, geometric mean, and geometric coefficient of variation.

Descriptive statistics of PK parameters (a.o. Min, Median, Max) will be tabulated by cohort.

7.6.2 Further endpoints phase IIa

All summary statistics are provided by treatment arm.

7.6.2.1 Successful virus isolation from nasopharyngeal swabs in SARS-CoV-2-infected individuals

Information will be shown for each assessment time point on whether live virus could be isolated in participating subjects or not. In addition, the relative frequency of positive samples will be shown per timepoint.

This endpoint will be evaluated on subjects from the subject set TS.

7.6.2.2 SARS-CoV-2 RNA shedding in oropharyngeal swabs determined by qRT-PCR in SARS-CoV-2-infected individuals

The same evaluations as proposed to be done for the secondary endpoint of SARS-CoV-2 RNA shedding in nasopharyngeal swabs determined by qRT-PCR in SARS-CoV-2-infected individuals shown in [Section 7.5.2.2.3](#) will be implemented for this endpoint. These evaluations will be based on all subjects in the subject set TS who have at least a baseline value and a second measurement in the respective time period of viral RNA shedding in OP swabs by qRT-PCR.

7.6.2.3 Successful virus isolation from oropharyngeal swabs in SARS-CoV-2-infected individuals

Information will be shown for each assessment time point on whether live virus could be isolated in participating subjects or not. In addition, the relative frequency of positive samples will be shown per timepoint.

This endpoint will be evaluated on subjects from the subject set TS.

7.6.2.4 Frequency of COVID19-related hospitalization and medically-attended health care contacts in SARS-CoV-2-infected individuals not previously hospitalized

Subjects will be categorised into having a hospitalisation or medically-attended health care contact over 29 days. Descriptive summary statistics by treatment group will be provided for this endpoint.

This endpoint will be evaluated on subjects from the subject set TS.

7.6.2.5 Time to resolution of self-assessed SARS-CoV-2-related symptoms

A log-rank test will be used to evaluate the effect of DZIF-10c on time to resolution of self-assessed SARS-CoV-2-related symptoms compared to Placebo over 29 days. A Cox proportional-hazards model will be used to derive the hazard ratio and 95 % CI between each of the two randomised treatment regimens that were assigned DZIF-10c and the placebo regimen (Hazard ratios <1 will favour DZIF-10c). This will be done for each symptom (cough, feverishness, body ache, headache, sore throat, shortness of breath, loss of taste or smell) separately as well as together for all symptoms. Breslow's method for handling ties will be used. Kaplan-Meier plots by treatment group will also be presented and the rates at day 29 compared.

This endpoint will be evaluated on subjects from the subject set TS.

7.6.2.6 Differences of viral spike gene sequences obtained before and after study drug administration and the investigation of the effect of observed mutations on viral sensitivity to DZIF-10c in neutralization assays

These analyses will be performed by UKK and reported in a separate report which will be appended to the CTR.

7.6.2.7 The activity and frequency of SARS-CoV-2-reactive immune cells following DZIF-10c administration

As described in Section 4, these analyses will be performed by UKK and will not be included in the CTR but might be reported elsewhere.

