5.3.5 Time to resolution of self-assessed SARS-CoV-2-related symptoms

Date of symptom assessment for an individual subject and symptom will be obtained from the subject diary for every symptom (namely: cough, feverishness, body ache, headache, sore throat, shortness of breath, change in/loss of taste and smell) separately. Symptom evaluation scoring will take place every day on a 4-point scale (0=absent; 1=mild; 2=moderate; 3=severe), and the results entered in a subject diary. Date of resolution on the 4-point scale will be defined as the first day after drug intake where a SARS-CoV-2-related symptom is recorded as “0”. Any subsequent reoccurrence will not be considered.

For subjects with known date of symptom resolution within the first 28 days after drug intake the derivation will be as follows:

- Time to resolution [days] = Date of resolution of symptom – date of drug intake + 1

Subjects who did not experience any resolution of their existing symptom by day 29, or who have missing evaluation data, or who did not show a particular symptom at baseline will be censored according to the mechanism for censoring as described in [Table 5.3.5: 1](#) below. In particular, all subjects with no symptom at baseline will be censored at day 1, even if they later develop a symptom (after drug intake).

Table 5.3.5: 1 Censoring and Event Rules for Time to resolution of self-assessed SARS-CoV-2-related symptoms within the first 28 days after drug intake.

Rule #	Situation	Outcome (event or censored)	Date of event or censoring
1	Subject had a symptom at baseline and a resolution within the first 28 days and date of resolution is known	Event	Date of event
2	Subject had a symptom at baseline and a resolution within the first 28 days and date of resolution is unknown	Event	Imputed date of event
3	Subject had a symptom at baseline but no resolution within the first 28 days	Censored	Day 29 (28 days after first drug intake)
4	Subject had a symptom at baseline but resolution status within the first 28 days is unknown or a subject has missing assessment data	Censored	Date of last recorded consecutive follow-up entry of symptom status within the first 28 days after drug intake
5	Subject did not show a particular symptom at baseline	Censored	Day 1 (Date of drug intake)

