9.2.2.2 Cox proportional-hazards model

Time to resolution of self-assessed SARS-CoV-2-related symptoms:

```
#####
ods output ParameterEstimates = param_est_raw GlobalTests = global_test_raw;
title "Unstratified cox model";
PROC PHREG DATA= tte_analysis_allpat ;
  CLASS trt01p (REF = "Placebo") ;
  MODEL ady * cnsr(1) = trt01p /TIES = BRESLOW;
  HAZARDRATIO trt01p /CL = WALD ALPHA = 0.05;
  ODS OUTPUT HAZARDRATIOS = hazard_raw;
RUN;
ods output close;
#####
```

Where:

- cnsr = censoring variable (1=censored)
- trt01p = treatment arm
- ady = analysis day

Note that the reference level in the code above (“Placebo”) has to be adapted to the level used in the study, and that the evaluation has to be implemented for each symptom separately.

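### The SAP reads the hazard ratio for time to symptom resolution the wrong way round: a value below 1 means slower resolution on DZIF-10c; its tie method also pulls the estimate towards no effect

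*SAP*

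**What the plan says.** SAP 7.6.2.5 compares time to resolution between each of the two DZIF-10c regimens and placebo by log-rank test and Cox model, for seven symptoms separately and for all of them together. It gives the reading rule "Hazard ratios <1 will favour DZIF-10c" and names Breslow's as the method for ties. Kaplan-Meier plots and a comparison of the day-29 rates accompany the model.

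SAP 5.3.5 defines the event. The date of resolution "will be defined as the first day after drug intake where a SARS-CoV-2-related symptom is recorded as" zero. In Table 5.3.5: 1, rule 1 ("Subject had a symptom at baseline and a resolution within the first 28 days and date of resolution is known") is an event, and rule 3 (symptom at baseline, no resolution in 28 days) is censored at day 29.

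The sample code in SAP 9.2.2.2 has "MODEL ady * cnsr(1) = trt01p /TIES = BRESLOW" with "cnsr = censoring variable (1=censored"), and sets placebo as the reference level of the treatment variable.

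**The concern.** In most survival analyses the event is harmful and a hazard ratio below 1 is good news. Here the event is the end of a symptom, so the usual reading has to be turned round, and the SAP has not done so. If the report follows the rule, a regimen that shortens symptoms is described as worse than placebo, and one that prolongs them as better. The same rule governs 8 analyses × 2 regimens = 16 hazard ratios. The trial is meant to generate hypotheses for later studies, so the direction of an effect is a large part of what it can contribute.

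The tie method is a separate and lesser matter. Resolution times are whole days within a 28-day window, so many participants share an event time. With heavy ties the Breslow approximation pulls the hazard ratio towards 1.

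**Working it through.** The documents give no expected hazard ratio, event count or median for this endpoint, so there is no planned figure to reproduce.

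**Direction.** This follows from the SAP alone:

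1. Event: resolution (5.3.5; Table 5.3.5: 1, rules 1 and 2). Non-resolution is censored (rule 3).
2. Code: a value of 1 marks censoring (9.2.2.2), so the modelled hazard is the rate of resolution.
3. Reference level: placebo (9.2.2.2), so HR = resolution rate on DZIF-10c / resolution rate on placebo.
4. HR > 1 therefore means faster resolution on DZIF-10c, and HR < 1 slower.

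As an illustration, take exponential times and an assumed placebo median of 6 days. Then median on DZIF-10c = 6 / HR:

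- HR = 1.5: 6 / 1.5 = 4.0 days, shorter than placebo.
- HR = 0.67: 6 / 0.67 = 9.0 days, longer than placebo. The SAP would call this favourable to DZIF-10c.

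The stated rule would be right only for a placebo/DZIF-10c ratio or for a harmful event. The reference level excludes the first and Table 5.3.5: 1 excludes the second. No other section inverts the ratio.

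**Ties.** Inputs from the documents: daily diary scoring and censoring 28 days after intake (SAP 5.3.5), and 20 participants per arm (protocol 8.2). Assumed, because the documents give no values: exponential times, placebo medians of 3, 5 and 10 days, and true HRs of 1.5, 2 and 3. Times were rounded up to whole days and two-arm Cox models were fitted with each tie method, in 1,500 simulated trials per scenario. Hazard ratios below are exponentials of the mean log HR, for a true HR of 2 and 20 per arm:

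| Placebo median | Unrounded times | Breslow | Efron | ln(Breslow) / ln(Efron) | Events / distinct days |
|---|---|---|---|---|---|
| 3 days | 2.073 | 1.846 | 2.047 | 0.613 / 0.716 = 0.856 | 40.0 / 10.2 |
| 5 days | 2.057 | 1.916 | 2.044 | 0.650 / 0.715 = 0.910 | 39.6 / 13.5 |
| 10 days | 2.069 | 1.994 | 2.063 | 0.690 / 0.724 = 0.953 | 36.7 / 17.2 |

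The shrinkage of the log HR is thus about 14%, 9% and 5%. Over all nine scenarios at 20 per arm the Breslow/Efron ratio ran from 0.825 to 0.958, a shrinkage of about 4% to 18%. At 12 per arm it ran from 0.833 to 0.963.

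A large-sample check (1,000 per arm, true HR 2, 30 trials per scenario) removes small-sample effects. Breslow gave 1.799, 1.883 and 1.932; Efron gave 1.994, 2.010 and 1.997. The bias belongs to the Breslow approximation and not to the sample size.

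To put this in proportion, SE(log HR) ≈ √(4 / events):

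- 3 days: √(4/40.0) = 0.316; gap 0.716 − 0.613 = 0.103, about 0.33 SE.
- 5 days: √(4/39.6) = 0.318; gap 0.715 − 0.650 = 0.065, about 0.20 SE.
- 10 days: √(4/36.7) = 0.330; gap 0.724 − 0.690 = 0.034, about 0.10 SE.

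**The case against.** The sentence changes no estimate, confidence interval or test. The code returns a correct ratio against placebo, and the Kaplan-Meier curves and day-29 rates beside it would show the true direction, so an attentive author might notice. The endpoint is exploratory, p-values are nominal, and symptom resolution is not among the outputs listed for either interim analysis (SAP 9.1.1.3 and 9.1.2.3). All of this stands. It makes the consequence a risk of misreporting rather than a certain one, and no primary or secondary result, sample size or error rate depends on it. It does not make the sentence right, and a report that followed it could place curves showing faster resolution next to a ratio labelled as favouring placebo.

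On ties, Breslow is a recognised method, specified consistently in text and code. It never reverses the sign here, and it leaves the log-rank test and the Kaplan-Meier rates untouched. The size of the shrinkage rests on assumed medians and hazard ratios. The gap is at most about a third of a standard error in the scenarios tabulated. Participants without a given symptom at baseline are censored at day 1, so the informative numbers per symptom will be below 20 per arm and the standard error larger still. This too stands: the tie method alone would be a minor remark.

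It can also be asked whether Efron is the right yardstick, since at 20 per arm it averages slightly above the true value of 2. The fit to unrounded times does the same (2.06 to 2.07), so that excess is a small-sample effect and not an effect of tie handling. At 1,000 per arm Efron sits within 0.01 of 2 and Breslow does not.

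**Conclusion.** The concern holds. The direction rule in SAP 7.6.2.5 is the reverse of what the SAP's own event definition and code imply, and this rests on no outside assumption. It should be corrected before symptom results are reported. The reversal is complete and covers all 16 hazard ratios, although the estimates would be correct.

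The tie method is secondary. Breslow was closer to 1 than Efron in every scenario run, by about 4% to 18% of the log hazard ratio at 20 per arm. The amount depends on the assumed medians, effect sizes and exponential times: it is small when resolution is slow and larger when resolution is fast or the effect is strong.

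**What to change.** In SAP 7.6.2.5, replace the reading rule with: hazard ratios (DZIF-10c versus placebo) above 1 favour DZIF-10c, meaning faster resolution. Label the tables and figures to match. This is a logical correction that cannot be driven by the data, and it costs one sentence.

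In 7.6.2.5 and 9.2.2.2, change the tie method from Breslow to Efron. This is one word in the text and one keyword in the code. Record that the change was made without reference to symptom results by arm.

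A small addition while the code is open: the log-rank sample in 9.2.2.1 requests only one global test over the three arms, whereas 7.6.2.5 speaks of a comparison with placebo. SAP 9.2 already allows the sample code to be adapted, and the Cox model gives each regimen against placebo, so this is a tidy-up. Adding DIFF=CONTROL with placebo as the control makes the code match the text.
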